## 4.1 Enrolment/Screening Period

Procedures will be performed according to the Study Plan [Table 1](#).

At Screening, consenting patients are assessed to ensure that they meet eligibility criteria. Patients who do not meet these criteria must not be enrolled in the study.

The below assessments to be performed for all enrolled patients at Visit 1:

- Contact IVRS/IWRS to obtain unique patient enrolment number
- Perform an ophthalmology examination (if not performed within previous 12 months)
- Review and confirm the patient's eligibility for the study by assessing inclusion and exclusion criteria listed in Sections [3.1](#) and [3.2](#)
- Dispense patient electronic diary and provide instruction on recording the values
- Patient medical and surgical history (including VOC over previous 12 months) as well as medication history (last 3 months) will be obtained with the review of selection criteria
- Record demographics (including sex, date of birth, race, ethnic group)
- Obtain vital signs (pulse rate and blood pressure [BP]), body weight and height
- Perform standard physical examination
- Perform 12-lead electrocardiogram (ECG). ECG must be obtained and reviewed with no significant abnormalities prior to randomisation
- Obtain specimens (blood) for safety laboratory panel and virology screen, and perform serum pregnancy test for females of child bearing potential
- Obtain specimen for urinalysis
- Review concomitant medications and AEs including bleeding events
- Obtain study drug dispensing bottles assignment numbers by accessing IVRS/IWRS and dispense the study drug bottles
- The patient will take his/her first dose of the run-in period study drug

Dispense the patient participation card and schedule the Visit 2 date. Remind patient to bring electronic diary (eDiary) during their next scheduled visit. Patients should be instructed to not take their dose at home in the morning of Visit 2 and to return the unused study drug.

## **4.2 Treatment period**

Descriptions of the procedures for this period are included in the Study Plan [Table 1](#). The specific requirements to be followed during treatment period are mentioned below:

### **4.2.1 Visit 2, Randomisation**

- Review and confirm inclusion/exclusion criteria for randomisation
- Patient eDiary will be collected from those who do not qualify for randomization
- Review concomitant medications and AEs including bleeding events
- Collect and assess compliance with run-in study drug based on tablet count
- Obtain vital signs (pulse rate and BP)
- Perform urine pregnancy test for females of child bearing potential
- Perform platelet aggregation measurement by using VerifyNow™ P2Y12 assay and reported as PRU (prior and 2 hours post-dose)
- Obtain specimens (blood) for biomarker analysis prior to study drug dispensing (only if patient agrees to consent for optional biomarker research)
- Contact IVRS/IWRS to randomise patient and obtain study drug dispensing bottles assignment number and dispense the study drug bottles
- Patient will be administered his/her first dose of the double-blind treatment at site
- A PK sample will be collected 2 hours post-dose

Schedule the Visit 3 date. Remind patient to bring eDiary in the next scheduled visit and instruct to not take their dose at home in the morning of Visit 3 and bring the study drug to clinic. After all the above assessments patients are allowed to leave the clinic.

### **4.2.2 Visit 3, treatment visit**

- A PK sample will be collected 0 hr (pre-dose) and at 2 hours post-dose
- Review concomitant medications and AEs including bleeding events
- Obtain vital signs (pulse rate and BP)
- Perform platelet aggregation measurement by using VerifyNow™ P2Y12 assay and reported as PRU (prior and 2 hours post-dose)
- Obtain specimens (blood) for biomarker analysis

- Patient will be administered his/her Visit 3 morning dose at site

Schedule the Visit 4 date. Remind patient to bring eDiary and to return the unused study drug during their next scheduled visit.

#### **4.2.3 Visit 4, treatment visit**

- Review concomitant medications and AEs including bleeding events
- Collect and assess compliance with study drug based on tablet count
- Obtain vital signs (pulse rate and BP)
- Obtain specimen for urinalysis and perform urine pregnancy test for females of child bearing potential
- Obtain specimens (blood) for safety laboratory panel and biomarker analysis
- Contact IVRS/IWRS to obtain study drug dispensing bottles assignment number and dispense the study drug bottles

Schedule the Visit 5 date. Remind patient to bring eDiary and to return the unused study drug during their next scheduled visit.

Patients should be contacted by telephone between Visits 4 and 5 (at Week 8 at a minimum), and Investigators are expected to follow subjects per local institutional guidelines during this period. If unscheduled visits are required for AEs or medical complications, please see Section [4.2.5](#).

#### **4.2.4 Visit 5, End of treatment visit**

- Patient eDiary will be collected
- Review concomitant medications and AEs including bleeding events
- Obtain vital signs (pulse rate and BP), body weight
- Perform standard physical examination
- Obtain specimens (blood) for safety laboratory panel
- Obtain specimen for urinalysis and perform urine pregnancy test for females of child bearing potential
- Collect and assess compliance with study drug based on tablet count

Instruct the patient that they will be contacted for safety assessment through telephone after 2 weeks.

#### **4.2.5      **Unscheduled visits****

Patients may return to the clinic for an unscheduled visit. At these visits, patients should be evaluated according to the Investigator's standard practice, and the Investigator will determine whether the patient is well and stable enough to continue on study medication. The Investigator's evaluation should be documented in the source documents. Unscheduled visits should not affect the regular visit schedule and assessments.

The following are suggested to be performed at unscheduled visits, per the Investigator's discretion, and entered in the eCRF:

- Review concomitant medications and AEs including bleeding events
- Perform standard physical examination
- Obtain specimens (blood) for safety laboratory panel
- Perform other diagnostic tests as needed based on the patient's condition

#### **4.3        **Follow-up period****

Visit 6 is safety follow-up visit, during which all patients will be contacted by telephone by site personal to check their concomitant medications and for any AEs including bleeding events.

### **5.         **STUDY ASSESSMENTS****

The Web Based Data Capture (WBDC) system will be used for data collection and query handling. The Investigator will ensure that data are recorded on the eCRF as specified in the study protocol and in accordance with the instructions provided.

The Investigator ensures the accuracy, completeness, and timeliness of the data recorded and of the provision of answers to data queries according to the Clinical Study Agreement (CSA). The Investigator will sign the completed eCRF. A copy of the completed eCRF will be archived at the study site.

#### **5.1        **Efficacy assessments****

Clinical efficacy events will be collected in the eCRF and by using a daily eDiary. These events will be identified using standard questioning of the patient at each visit, by information collected in the eDiary or by information that the Investigator may receive as part of standard medical practice.

##### **5.1.1     **PRO****

Pain is commonly reported in clinical trials by having patients provide a rating of their own pain, i.e., it is patient reported.

The primary efficacy variable is change from baseline in number of days with pain. Secondary and exploratory variables include intensity of Worst Pain and use of analgesics. Patient reported data regarding Average Pain, Pain Right Now and Absence from school/work are exploratory variables.

#### **5.1.1.1 Pain due to SCD**

Pain assessment will be captured daily using an eDiary and will be collected in the evening from enrolment to end of treatment. After the enrolment part only patients with  $\geq 4$  days of pain during last 4 weeks of the run-in period will be eligible for randomisation.

At the start of the study, Visit 1, patients will be issued an eDiary. The numerical rating scale (NRS) asks the patient to rate the intensity of his/her worst pain and average pain during the past 24 hours and pain right now, using an 11-point scale where 0 represents “no pain” and 10 represents “pain as bad as you can imagine”. The patient will indicate his/her pain intensity by tapping a number on the NRS scale on the screen in the eDiary. If a patient reports 0 (no pain) that will be recorded as a pain free day, whereas a report between 1-10 will be recorded as a day with pain.

The validity of the NRS has been well documented in different pain populations. The NRS demonstrates positive and significant correlations with other measures of pain intensity (Jensen et al 1986, Jensen et al 1989, Kremer et al 1981, Seymour 1982, Wilkie et al 1995). It has also demonstrated sensitivity to treatments that are expected to have an impact on pain intensity (Chapman et al 2001, Paice et al 1997, Stenn et al 1979).

If the patient answers that he/she has pain, a body outline diagram will be presented and the patient will be asked to indicate the location of the pain.

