### Study design

This is a randomised, double-blind, double-dummy, parallel-group, placebo-controlled, study evaluating 2 doses of ticagrelor in 90 patients aged 18 to 30 years, with sickle cell disease (SCD). Patients will start with a 4-week single-blind double-dummy placebo run-in period to determine the frequency of days with pain at baseline using an electronic diary (eDiary) every day. Approximately 180 patients will be enrolled for the run-in period in order to provide 90 patients meeting criteria for randomisation. Patients with  $\geq 4$  days of pain during last 4 weeks of the run-in period will be eligible for randomisation. Patients will then be randomised to double-blind double-dummy treatment period in a 1:1:1 ratio (30 to each treatment group) to receive ticagrelor 10 mg twice daily (bid), or 45 mg bid, or placebo bid for 12 weeks. Patient will be followed for safety assessment during and after 2 weeks of treatment completion.

During the 12 week treatment period, patients will complete a daily eDiary concerning daily pain intensity, pain location, use of analgesics and absence from school or work. At the end of the study patients will be asked to rate the change in their sickle cell pain compared to baseline. Platelet aggregation will be measured and reported as P2Y12 reaction units (PRU) pre-dose and 2 hours post-dose at the randomisation and 1 week post randomisation. Pharmacokinetic (PK) parameters will be measured at 2 hours post-dose at randomisation; and pre-dose and at 2 hours post-dose, 1 week post randomisation. Biomarkers will be assessed pre-dose at randomisation, at 1 week and 4 week post randomisation. During the study, patients will be evaluated for adverse events (AEs) including bleeding and vaso-occlusive crisis (VOC).

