### **3.1 Inclusion criteria**

For inclusion in the study patients should fulfil the following criteria:

1. Provision of signed and dated written informed consent prior to any study specific procedures not part of standard medical care.
2. Male and female young adults aged  $\geq 18$  to  $\leq 30$  years (at Visit 1), with confirmed medical history or diagnosis of homozygous sickle cell (HbSS) or sickle beta-zero-thalassaemia (HbS/ $\beta^0$ ) by HPLC.
3. If treated with an anti-sickling agent such as hydroxyurea, dose must be stable for 3 months before enrolment.

At Visit 2 only - randomisation criteria:

4. Prior to dosing on Day 1, Visit 2, a negative serum pregnancy test performed at Screening (Visit 1) and a negative urine pregnancy test (dipstick) from Visit 2 must be available (for females).
5. Patient must have  $\geq 4$  days of pain during last 4 weeks of the single-blind run-in period to enter double-blind randomisation period.

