### **8.2 Sample size estimate**

A sample size of 30 patients per group provides the ability to detect a difference in proportion of days with pain of 0.17 (17 percentage points) by use of a 90% confidence interval. Basis for this assumption is a placebo level of 0.56 with a SD of approximately 0.4 (PISCES and a prasugrel study in both cases – [Wun et al 2013](#), [Smith et al 2008](#)).

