## **8.4 Outcome measures for analyses (Not Applicable)**

### **8.5 Methods for statistical analyses**

No statistical comparisons are planned for the primary objective. PRO and safety measures will be summarized descriptively using respective analysis set.

In general, all efficacy, safety, plasma concentrations of ticagrelor and active metabolite, PRU and PRO variables will be presented using descriptive statistics and graphs as appropriate. Continuous variables will be presented with descriptive statistics (n, mean, standard deviation [SD], median, min, max), within treatment group. Geometric mean and coefficient of variation (CV) will be used instead of arithmetic mean and SD, if appropriate, with CV(%) calculated as:

$$100 \cdot \sqrt{(\exp(s^2) - 1)}$$

where s is the SD of the data on a log scale.

Categorical variables will be summarized in frequency tables (number of patients and percentage), by treatment group. Data will also be presented in individual patient listings.

The presentation of pain, intensity of pain and days of analgesic use due to SCD, will be presented by week. They will also be presented by subgroup of PGIC, divided into 3 groups, improved (1 and 2), no change (3, 4 and 5) and worse (6 and 7).

In general, baseline values will be the closest observation prior to the first administration of randomised IP. For the baseline value of pain, intensity of pain and days of analgesic use, a mean value for the 4 weeks in the Screening period will be calculated.

The number of days with pain due to SCD and the analysis of analgesic use due to SCD will be analysed using an ANCOVA model, with treatment, country, baseline average value, and baseline hydroxyurea (HU) use as explanatory variables, and treatment and HU as fixed effects and centre as a random effect. Least squares differences in means between ticagrelor 45 mg and placebo and ticagrelor 10 mg and placebo with corresponding 90% confidence interval will be presented. The objectives will be analysed as a proportion of days, during the whole treatment period. A sensitivity analysis of pain and analgesic use will be performed using the ANCOVA model but excluding country and baseline HU use.

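### Counting any rating of 1-10 as a pain day hides partial relief from the primary measure, and section 8.5 gives pain intensity no between-group estimate

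*Protocol*

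**What the plan says.** - **Definition of a pain day** (protocol 5.1.1.1). Pain is rated each evening on an 11-point scale. A 0 is a pain-free day, "whereas a report between 1-10 will be recorded as a day with pain".
- **Primary variable** (5.1.1). "The primary efficacy variable is change from baseline in number of days with pain". Section 8.5 sets the scale: "The objectives will be analysed as a proportion of days, during the whole treatment period".
- **Selection** (3.1, criterion 5). A patient needs at least 4 "days of pain during last 4 weeks of the single-blind run-in period to enter double-blind randomisation period". There is no upper limit.
- **Planning values** (8.2). "A sample size of 30 patients per group provides the ability to detect a difference in proportion of days with pain of 0.17", using a 90% confidence interval. "Basis for this assumption is a placebo level of 0.56 with a SD of approximately 0.4". The section does not say whether these values describe patients before or after the 4-day selection.
- **Intensity** (2.2, 8.5). Intensity of pain is the first secondary objective, framed as ticagrelor versus placebo. Section 8.5 gives the ANCOVA, with least squares differences and 90% intervals, to days with pain and to analgesic use. Intensity is only presented by week and by subgroup of the patient's global impression of change.

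**The concern.** The eDiary collects a graded rating every day, but the primary measure keeps only whether it is above 0. A day that improves from 8 to 4, or from 4 to 2, counts exactly as before. Criterion 5 removes patients with few pain days and keeps those with pain on nearly all days, so some of the sample probably starts close to the top of the scale.

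If ticagrelor makes pain milder without abolishing it, the difference in proportion of days with pain could sit near zero. The outcome that would show the benefit, intensity, would then have no estimated treatment difference and no interval in section 8.5. Readers would have to judge a secondary objective versus placebo from weekly summaries by arm.

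**Working it through.** **1. The plan's own figure.** Inputs from 8.2: 30 per group, SD 0.4, 90% interval.

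Half-width = 1.645 × 0.4 × √(2/30) = 0.170.

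The stated 0.17 reproduces as the half-width of the interval for a difference between two arms.

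**2. Is a ceiling plausible?** At mean 0.56 the largest SD possible for a proportion is √(0.56 × 0.44) = 0.496. The assumed 0.4 is 0.4/0.496 = 81% of that, so the values are widely spread towards the ends. If 0.56 and 0.4 described patients already selected (proportion at least 4/28 = 0.143), the largest SD would be √((0.56 − 0.143) × 0.44) = 0.428.

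**3. How large could it be?** Assume that 0.56 describes unselected entrants and that their true proportions follow a beta distribution, with φ = 0.2464/SD² − 1, a = 0.56φ and b = 0.44φ. Run-in pain days are binomial over 28 days, and patients with at least 4 are kept.

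| SD before selection | a, b | Pass criterion 5 | At least 27/28 among those kept |
|---|---|---|---|
| 0.40 | 0.302, 0.238 | 74% | 43% |
| 0.35 | 0.566, 0.445 | 82% | 25% |
| 0.30 | 0.973, 0.765 | 89% | 14% |

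At SD 0.40, 34% of those kept have pain on all 28 days. Their mean proportion is about 0.75 and the SD about 0.29.

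**4. What the mean and SD fix on their own.** With no shape assumed, and 0.56 and 0.4 taken to describe randomised patients, linear-programming bounds on the share with pain on at least 95% of days run from 0% to 51%. The protocol's expected yield of 90 randomised from 180 enrolled (50%) does not settle it, because it covers every reason for screen failure.

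**5. Direction depends on how the drug works.** This is an illustrative daily-rating model: patient mean severity normal (1.0, SD 3.5), day-to-day SD 1.5 to 2.5, and the same 4-day selection.

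| Assumed effect | Change in any-pain days | Change in days at 4 or more |
|---|---|---|
| Severity cut by 30% every day | 0.02 to 0.03 | 0.13 to 0.15 |
| 30% of pain days turned to 0 | 0.19 to 0.22 | 0.10 |

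The second row agrees with simple arithmetic: 0.30 × 0.75 = 0.225 at the post-selection mean from step 3. Mean daily rating falls by about 30% in both rows, because either each day's value or the number of days contributing is cut by 30%. It is the one summary that responds to both mechanisms.

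**6. Effect on the planning SD.** If 0.4 is a pre-selection value and the beta assumption holds, the half-width becomes 1.645 × 0.29 × √(2/30) = 0.12, before baseline adjustment.

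**The case against.** The strongest defence is that the endpoint matches the objective. The primary aim is fewer days with pain, section 1.3 describes the hoped-for benefit as less frequent daily pain, and the earlier prasugrel trial is cited for a trend in the same measure. Occurrence as primary and intensity as secondary is a coherent choice, and step 5 shows it is the better choice if the drug prevents painful days. This stands, and it is why the primary variable should not change.

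It can also be said that partial relief is captured elsewhere: intensity by arm and week, analgesic days with the same ANCOVA, and the global impression of change. Section 8.1 also defers detail to an SAP that is not shown. This stands in part. But section 8.5 does not merely leave intensity open: it names the outcomes that receive the model and puts intensity under presentation.

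Three stronger readings are tempting and not supported:

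- **That about 40% of patients start at the ceiling on the protocol's own numbers.** That needs a distribution shape, SD at the top of the range, and the reading that 0.56, which the protocol calls a placebo level, describes unselected entrants at run-in.
- **That the endpoint is saturated, or that ceiling patients cannot move.** They can improve by having pain-free days, and under the step 3 assumptions more than half of those randomised have at most 26 pain days. Insensitivity to partial relief comes from the cut between 0 and 1 and affects every pain day; it is not confined to ceiling patients.
- **That the trial would formally conclude no effect.** Section 8.5 plans no statistical comparison for the primary objective, only estimates with intervals.

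**Conclusion.** The point holds in limited form. By definition, and with no distributional assumption, the primary measure cannot register relief that stops short of zero on a day. A baseline ceiling is plausible. Its size, about 14% to 43% at 27 or 28 of 28 days, rests on the beta shape, on unselected entrants and on an SD between 0.30 and 0.40. Whether the primary measure under-reports or best reports benefit depends on a mechanism that the trial has not yet established. The correctable weakness is that section 8.5 provides no between-group estimate for intensity, so one of the two plausible forms of benefit would have no treatment difference or interval.

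The silence in section 8.2 on whether 0.56 and 0.4 apply before or after selection is a lesser matter. Clarifying it could work in the trial's favour, since the post-selection SD may be smaller than 0.4.

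**What to change.** 1. Keep the primary variable and its definition.
2. In section 8.5, extend the same ANCOVA (least squares mean differences for each dose against placebo, 90% intervals, run-in value as baseline) to mean daily worst-pain rating over the treatment period.
3. As a supportive analysis, apply it also to the proportion of days with worst pain at or above one higher cut. Fix and justify the cut before unblinding. The figure of 4 used above is only an illustration; the protocol gives no basis for a particular value.
4. In section 8.2, state whether 0.56 and 0.4 apply before or after the 4-day selection and, if before, give the values expected after it.

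If the SAP already contains items 2 and 3, only the protocol wording needs aligning. The cost is one or two more supportive estimates to report and a cut to defend in advance. The ratings are already in the eDiary, so no patients, visits or assessments are added.

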#### **5.1.1.2 Use of Analgesics**

During both the enrolment and treatment part, patients will be asked about their use of analgesics. The question ‘Have you taken any medication because of your SCD pain today’ will be administered daily in the electronic device. Response options will be dichotomous, i.e., ‘Yes’ or ‘No’. The question is presented in the eDiary and should be answered daily in the evening. Specification of whether analgesics have been opioid or non-opioid will be done at follow-up site visit.

#### **5.1.1.3 Absence from school/work**

Absence from school/work will be recorded in the eDiary weekly by asking the question ‘Have you been at home from school/work the last 7 days because of your disease’. If the reply is ‘Yes’ the patient will be prompted to answer how many days he/she has been absent. Days off school/work due to study visits will not be recorded.

